8.1. Subject Disposition, Demographic and Baseline Characteristics

Subject disposition will be presented for all subjects in the ITT population. The number of subjects who completed the study and discontinued from the study will be provided. The reasons for early discontinuation at any point also will be presented by treatment group. Additionally, the number of weeks on study and study drug will be summarized for all treated subjects.

Demographic data and baseline characteristics, including age, gender, race, ethnicity, VOC history, Baseline Hb, Baseline SCDSM TSS, Baseline absolute reticulocyte, and Baseline reticulocytes %, will be summarized using descriptive statistics. This information will be reviewed for baseline differences, but no statistical testing will be performed.

Medical/surgical history and adverse events will be coded using the Medical Dictionary for Regulatory Activities (MedDRA) version 19.1 for the entire period of the study.

Medical/surgical history and adverse events will be summarized in tables and may be presented in data listings.

Prior and concomitant medications will be coded using the World Health Organization (WHO) Drug Dictionary (version WHO-DD01Sep2016) for the entire period of the study. Prior and concomitant medications will be summarized in tables and may be presented in data listings.

8.2. Efficacy Analysis

8.2.1. Primary Endpoint

8.2.1.1. Primary Analysis of Hemoglobin Response

For the primary analysis of Hb response, individual subject data through Week 24 will be included.

The Hb response rate will be analyzed using an exact Cochran-Mantel-Haenszel (CMH) general association test with imputation rules outlined in [Section 6.3.5](#). Each voxelotor dose group (900 mg and 1500 mg) will be compared to placebo while stratifying for the randomization stratification factor of HU use, age group and geographic region. Sample SAS code for the exact CMH general association test will be similar to the following:

```
PROC LOGISTIC;  
  CLASS treatment/PARAM=REF;  
  FREQ count;  
  MODEL response = treatment;  
  STRATA stratum;  
  EXACT treatment;  
RUN;
```

8.2.1.2. Additional Analysis of Hb

Change from baseline in Hb over time up to Week 24 will be analyzed using a mixed effect for repeated measures (MMRM) model. The fixed effect terms include treatment, study visit, treatment by visit interaction, HU use at baseline, age group and geographic region. Baseline Hb will be a co-variate. Within-subject variability will be modeled using an unstructured covariance matrix. Missing data due to early drop out or missed visit will not be imputed for this analysis. Missing data due to VOC, VOC hospitalization or RBC transfusion will be imputed, as described in [Section 6.3.5](#).

Change from baseline in hemoglobin up to Week 48 and Week 72 will be analyzed similarly with available data as of the clinical cutoff date for the primary analysis.

The adjusted mean (lsmean) change from baseline in Hb at each visit, estimated from the MMRM model, with the estimated standard error and 95% confidence interval (CI), will be presented in tabular and graphic format. The difference in the adjusted means between treatment groups and the associated 95% CI of the difference will be provided.

Hb worsening will be summarized using a shift table for each treatment group. Incidences of post-baseline Hb < 5.5 g/dL will be summarized by treatment group, as well as incidences of Hb change from baseline < -2 g/dL.

Proportion of subjects with Hb of ≥ 10 g/dL at Week 24 will be explored.

All analyses specified above will be based on data with imputation for RBC transfusion, VOC and VOC hospitalization, as applicable. The analysis of Hb response rate will also be repeated using observed data without imputation to assess the robustness of the data.

8.2.2. Secondary Endpoints

Unless otherwise specified, data will be analyzed with respect to Week 24. Data summaries beyond Week 24 will be tabulated.

8.2.2.1. Change from Baseline to Week 24 in Hemolysis Related Measures

Percent change from baseline over time up to Week 24 in unconjugated bilirubin, absolute reticulocyte, reticulocytes %, and LDH will be analyzed with a similar MMRM model and summarized in tabular and graphic format as for change from baseline to Week 24 in Hb.

In addition, the absolute and percent changes from Baseline to Week 24 in each hemolysis measure, including absolute reticulocyte, reticulocytes %, and unconjugated bilirubin will be presented descriptively via tabulation of descriptive statistics by treatment group.

If any of the laboratory measures reported are below the lower limit of quantitation or above the upper limit of quantitation, then the numerical limit will be used in the MMRM modeling and the tabulation of the descriptive statistics.

8.2.2.2. VOC up to Week 72

The number of VOC events will be modeled using a negative binomial model with the independent variable of treatment group and adjusted for the stratification factors used for randomization. Additional risk factors, including number of VOC occurrences during the 12 months prior to randomization, will also be explored.

The mean cumulative function of VOC events will be presented using recurrent events analysis methods.

Annualized incidence rate will be summarized for each treatment group.

These analyses will be repeated in a follow up analysis when all subject reaches 72 weeks of study participation or discontinues from the study early.

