6.3.2. Examination of Subject Subsets

Subgroups defined by subject age group, (adolescent, 12 to <18 years; and adults, 18 to 65 years), geographic region (North America, Europe, Other), baseline HU use (yes, no), baseline VOC history (1, >1) will be analyzed to evaluate the internal consistency of the study outcomes. Subgroups defined by baseline Hb level will also be explored.

In addition, comparability of study cohorts (e.g., Group 1, Group 2a, Group 1 & 2a, and Group 2b) will be assessed. Specifically, descriptive statistics will be presented for each study cohort regarding the following:

- Demographics
- Baseline disease characteristics
- Subject disposition by study visit
- Rates of missing Hb assessment at Week 24

Hb response rate and Hb change from baseline in voxelotor treatment groups compared to placebo will also be summarized by study cohort.

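### Free improvement, low weight: the main VOC model omits prior-year VOC count, which is already collected; this costs some precision but not validity

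*SAP*

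**What the plan says.** SAP 5 lists the annualized VOC rate as a secondary endpoint. SAP 8.2.2.2 says that the VOC count "will be modeled using a negative binomial model with the independent variable of treatment group and adjusted for the stratification factors used for randomization". Those factors are HU use, region and age group (SAP 6.2). On VOC history the section adds: "Additional risk factors, including number of VOC occurrences during the 12 months prior to randomization, will also be explored". Two time-scaled summaries accompany the model: "The mean cumulative function of VOC events will be presented using recurrent events analysis methods" and "Annualized incidence rate will be summarized for each treatment group".

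VOC history is used elsewhere in the plan. Eligibility requires at least one documented VOC in the previous year (Protocol 3.1). SAP 8.1 lists it among the baseline characteristics ("including age, gender, race, ethnicity, VOC history, Baseline Hb"). SAP 6.3.2 makes it a subgroup factor: "baseline VOC history (1, >1) will be analyzed to evaluate the internal consistency of the study outcomes". For change in Hb, SAP 8.2.1.2 states: "Baseline Hb will be a co-variate".

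VOC is not among the nine ordered secondary tests in SAP 6.3.3. Protocol 8.4.1.2.2 describes the VOC model in the same terms as the SAP.

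**The concern.** A patient's recent VOC frequency is likely to be among the better predictors of later VOC frequency. In a negative binomial model, unexplained variation between patients goes into the dispersion and widens the interval for the treatment rate ratio. A prognostic count that is already in the database could remove part of that variation at no cost in patients.

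Only precision is at stake. Randomization protects the comparison whether or not the count is in the model. The VOC result will still be read beside the laboratory endpoints, because long-term VOC is a stated secondary objective (SAP 3).

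A smaller point concerns wording. The endpoint is a rate, while the readable model text speaks of a number of events and names no offset for follow-up time. At the cutoff, subjects still on study have at least 24 weeks of follow-up (SAP 2), treatment runs to 72 weeks (SAP 2.1), and leavers have less.

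**Working it through.** **Figures in the plan.** There is none for VOC. The only power statement is for Hb response: 10% vs 40%, about 90 per arm, two-sided alpha 0.0481, more than 95% power (SAP 6.1). Exact enumeration of Fisher's test gives 99.7%, so it reproduces, but it has no bearing on VOC.

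**Inputs from the documents.** 274 randomized 1:1:1, so 274/3 ≈ 91 per arm and 182 for 1500 mg vs placebo; prior-year count 1 to 10 (Protocol 6); follow-up from 24 to 72 weeks apart from leavers; dropout anticipated below 10% (Protocol 8.4.2).

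**Assumed inputs.** Placebo rate 1.5 to 3.5 per year; dispersion 0.5 to 1.0; true rate ratio 0.80; 8% dropout per arm, spread evenly; follow-up at the cutoff uniform over 24 to 72 weeks. Persistence is the correlation between a patient's underlying VOC risk in the prior year and on study, set at 25%, 50%, 75% or 100%. The stratification factors were not simulated.

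**Simulation.** Negative binomial maximum likelihood with three models: A, no offset; B, log follow-up offset; C, offset plus log prior-year count. Median standard errors of the log rate ratio at the cutoff in the base case (3 per year, dispersion 0.6, 1000 replicates):

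| Persistence | A | B | C | B/C (covariate) | A/B (offset) |
|---|---|---|---|---|---|
| 25% | 0.158 | 0.149 | 0.148 | 1.007 | 1.060 |
| 50% | 0.155 | 0.146 | 0.142 | 1.028 | 1.062 |
| 75% | 0.149 | 0.140 | 0.131 | 1.069 | 1.064 |
| 100% | 0.144 | 0.134 | 0.116 | 1.155 | 1.075 |

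The ratios are taken from rounded standard errors; before rounding, the covariate effect is about 0.5% at 25%, 2.7% at 50% and 15% at 100%. Mean estimates stayed between 0.79 and 0.81 in all models, so omission does not bias the result.

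**Range over the assumed rates and dispersions, at the cutoff.** Omitting the count raises the standard error by 0.3-1.0% at 25% persistence, 1.6-3.0% at 50%, 3-9% at 75% and 6-23% at 100%. At the 72-week repeat the range at full persistence is 7-27%.

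**In subjects, at 50% persistence.** 1.016² = 1.032 and 1.030² = 1.061. Then 0.032 × 182 ≈ 6 and 0.061 × 182 ≈ 11, so the gain is worth about 6 to 11 subjects.

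**In the interval, base case at 50%.** The 95% limits are 0.80 × exp(±1.96 × SE). With B (0.146) they are 0.601 and 1.065; with C (0.142) they are 0.606 and 1.057.

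**A stronger assumed link.** If the VOC rate is set proportional to the prior count to the power 0.5 or 0.8 (rates 2 or 3 per year), the covariate cuts the variance by 12-14% or 24-33%. In standard-error terms, 1/√0.88 = 1.07 and 1/√0.86 = 1.08; 1/√0.76 = 1.15 and 1/√0.67 = 1.22. The strength of the link therefore drives the answer, and the documents do not give it.

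**Offset, if none were used.** Across the scenarios the standard error at the cutoff is roughly 3-8% larger. With equal follow-up there is no bias. As an illustration only, with 10% dropout on active and 5% on placebo, mean full follow-up of 48 weeks and 24 weeks for leavers, the estimate is multiplied by (0.90 × 48 + 0.10 × 24)/(0.95 × 48 + 0.05 × 24) = 45.6/46.8 = 0.974.

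**The case against.** The case against has several parts.

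- **The adjusted analysis is already foreseen, and the gain may be trivial.** This stands in part. SAP 8.2.2.2 names the prior-year count, so the change mainly alters which model leads. At 50% persistence the interval barely moves. That supports low weight, not dropping the point.
- **Prior VOC is not a baseline in the sense that baseline Hb is.** This is fair. It is a chart-history count, and the on-study definition adds a 2-hour minimum and timely medical contact (Protocol 8.1.3). The Hb model is a useful comparison, not proof of inconsistency. If records capture only 60% of qualifying events, the base-case gain falls from 2.7% to 2.5% at 50% persistence and from 15% to 12% at full persistence.
- **The simulation omits HU use, age and region.** This stands. If they correlate with VOC history they would absorb some of the gain, so the figures may be too high.
- **Promoting the covariate changes the main model after 156 of 274 subjects (57%) were unblinded.** This stands, and it is why the change needs disclosure and the present model should be kept as a sensitivity analysis.

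A reader might also infer more than the documents support:

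- **That the plan lacks an offset.** The programming specifications (SAP 14) are redacted. The endpoint is a rate, and Protocol 8.4.1.2.2 and 8.4.2.3 speak of VOC rates. Only the readable model text is silent. Bias would need unequal follow-up between arms, which no passage reports.
- **That the counting interval is undefined.** SAP 4 counts events from randomization to end of study. The default in SAP 8.2.2, "Unless otherwise specified, data will be analyzed with respect to Week 24", yields to the section's Week 72 heading and its planned 72-week repeat.
- **That the choice of lead model is open.** SAP 8.2.2.2 already makes the stratification-only model the main one and marks the rest as exploration.

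**Conclusion.** The point holds as an optional, low-weight improvement. The planned model is valid; adding the prior-year count would make it somewhat more precise. The gain is negligible if VOC risk persists weakly from year to year, about 2-3% of the standard error at 50% persistence, and material (6-23%) only if persistence is near complete. All of these sizes rest on assumed VOC rates, dispersion and persistence. Nothing confirmatory depends on the choice. The offset is a request for clarity, not an error found in the plan.

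**What to change.** Edit SAP 8.2.2.2 only, before Group 2b is unblinded, which is the point by which SAP 2 says the SAP will be final:

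- Add log(prior-year VOC count) to the main negative binomial model beside treatment, HU use, age group and region, with any recorded zero set to 1.
- State a rule for a missing count so that no ITT subject is dropped, for example the median of the recorded counts taken without regard to arm.
- Use the count rather than the existing 1 vs >1 split, which recovers only 1.0-1.6% at 50% persistence and 3-8% at full persistence.
- Report the model without VOC history as a sensitivity analysis.
- State that the change was made after 156 of 274 subjects had been unblinded and before Group 2b was.
- Clarification: if the redacted specifications do not already do so, name as offset the log of time from randomization to the earlier of end of study or data cutoff, so that the modelled ratio matches the annualized endpoint.

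The cost is a few sentences and one extra model parameter. No new data or patients are needed. No protocol amendment is needed either, because the SAP supersedes the protocol's analysis text (SAP 2; Protocol 8).

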8.2.3. Exploratory Endpoints

8.2.3.1. Time to Event Analysis

Kaplan Meier methods will be used to summarize time-to-event endpoints, including time to first VOC, time to first ACS or pneumonia and time to first RBC transfusion. Event rates will be estimated at landmark time points, e.g., Week 12, Week 24, Week 48, as appropriate.

Rate of opioid use, and rate and reasons for RBC transfusion will be summarized descriptively by treatment group.

8.2.3.2. Patient-Reported Outcomes

PRO measures, including Sick Cell Disease Severity Measure, EQ-5D-L health questionnaire, Clinical Global Impression (CGI), will be summarized descriptively.

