2.2. Choice of Control Group

This study uses placebo as a comparator on the background of best clinical standard of care treatment. All approved therapies for SCD are allowed under this protocol, none are withheld. This includes pain control, hydroxyurea, L-glutamine and blood transfusions. Hydroxyurea (HU) dose should be stable for at least 90 days prior to signing the ICF to avoid confounding the interpretation of the safety and efficacy endpoint in this study. If HU is initiated after a participant has been randomized, the participant will be discontinued from the study.

Furthermore, the placebo group is needed to fully characterize the risks and benefits of voxelotor over the background of standard of care (HU), in particular for the key secondary electronic patient reported outcomes (ePRO) SCD Severity Measure (SCDSM) which requires a placebo group for interpretation for the meaningfulness of changes in symptoms.

Agreeing to placebo treatment does not place subjects at any increased risks because no standard of care therapies will be withheld as a result.

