8.4.1.2. Secondary Endpoints

8.4.1.2.1. Change from Baseline to Week 24 in Hemolysis Related Measures

Percent change from baseline over time in unconjugated bilirubin, absolute reticulocyte, reticulocytes %, and LDH will be analyzed with a similar MMRM model as for change from baseline to Week 24 in Hb.

In addition, the absolute and percent changes from Baseline to Week 24 in each hemolysis measure, including absolute reticulocyte, reticulocytes %, and unconjugated bilirubin will be presented descriptively via tabulation of descriptive statistics by treatment group.

8.4.1.2.2. VOC up to Week 72

The number of VOC events will be modeled using a negative binomial model with the independent variable of treatment group and adjusted for the stratification factors used for randomization. Additional risk factors, including number of VOC occurrences during the 12 months prior to randomization, will also be explored.

The mean cumulative function of VOC events will be presented using recurrent events analysis methods.

Annualized incidence rate will be summarized for each treatment group.

For Group 1 analysis, the proportion of days with SCD exacerbation will be analyzed by a fixed effects linear model. Change from Baseline in the TSS will be analyzed with an MMRM. The rate of VOC will be analyzed by the CMH row means scores test. Given the size and duration of the study at the time of the Group 1 Analysis, the recurrent event rate is expected to be low. However, negative binomial regression analyses will be performed if justified by the distribution of event rates.

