8.4.2.3. Total Symptom Score

- Missing data due to missing diary entries or participant dropout: If a participant has 7 or more missing diary entries unrelated to VOC or hospitalization due to VOC in a 4-week period, the TSS will be set to missing for that period. For the primary method of analysis of this endpoint (MMRM), missing at random (MAR) is assumed and no imputation will be done.
- Missing data due to VOC or hospitalization due to VOC: participant will be assigned the worst TSS score prior to the onset of the VOC or hospitalization due to VOC for each day that contributed to missing data.
- RBC transfusions: For the 8-week period (primary analysis) or 12-week period (sensitivity analysis) after the transfusion, the TSS from a 4-week period prior to transfusion will be used.

For the rate of VOC, the analyses will not make any adjustments due to missing data. Sensitivity analyses may be performed to test the robustness of inference to missing data. The imputation method will be informed by data from placebo participants with similar clinical status as those with missing data.

Additional details regarding handling of missing data will be described in the SAP.

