3. OBJECTIVES

Primary Objective:

The primary objective is to assess the effect of voxelotor as measured by improvement in hemoglobin, compared to placebo.

Secondary Objectives:

The secondary objectives include the following:

- To assess the effects of voxelotor as compared to placebo on clinical measures of hemolysis, including unconjugated bilirubin, absolute reticulocyte, reticulocyte %, and LDH.
- To assess the effects of voxelotor as compared to placebo on long term Vaso-Occlusive Crisis (VOC).

Exploratory Objectives:

The exploratory objectives are to evaluate the effects of voxelotor compared to placebo on the following:

- Sickle Cell Disease Severity Measure (SCDSM),
- EuroQol EQ-5D-5L™ health questionnaire (EQ-5D-5L™),
- Clinical Global Impression Scale (CGI),
- Measures related to SCD pathophysiology and their utility as pharmacodynamic markers, e.g.,
 - Laboratory and clinical outcome measures including albumin creatinine ratio, scleral icterus, cholecystectomy and leg ulcers
 - Exploratory measures including RBC deformability and inflammatory markers
- School and/or work attendance and the use of opioid during the treatment period as recorded via eDiary,
- Time to first RBC transfusion and post baseline onset of VOC.
- Measures predictive of response to voxelotor.

Safety Objectives:

The safety objectives are to assess the safety of voxelotor based upon AEs, SAEs and SCD-related AEs, including VOC, acute chest syndrome (ACS) and Pneumonia, priapism, and osteonecrosis.

In addition, RBC transfusions, clinical laboratory tests, physical examinations, and other clinical measure events (e.g., discontinuations due to AEs, dose reductions) will also be evaluated.

Pharmacokinetic Objective:

The PK objective is to further assess the PK profile of voxelotor as evaluated by population PK analysis.

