Hemoglobin (Hb) response is based on the difference between the average value of Hb levels at Week 20 (Hb20) and Week 24 (Hb24) and baseline Hb level (HbB). A subject is considered to be a Hb responder if $[\text{mean}(\text{Hb20}, \text{Hb24}) - \text{HbB}] > 1 \text{ g/dL}$. If Hb20 or Hb24 is missing, then the calculation will use the non-missing Hb level. Regardless of calculated difference, subjects will be classified as a non-responder if any of the non-responder criteria in [Section 6.3.5.1](#) are met.

Hemoglobin Worsening at Week 24

- Severe anemic episode - worst Hb between weeks 12 and 24 inclusive is $< 5.5 \text{ g/dL}$
- Acute anemic episode - worst Hb between weeks 12 and 24 inclusive, is $\geq 5.5 \text{ g/dL}$ and $< 7 \text{ g/dL}$

Rate of Opioid Use During Treatment Period

The rate of opioid use is calculated as the number of days opioids were taken for SCD symptom management (as recorded in the eDiary) divided by the number of days with non-missing eDiary data from date of randomization to date of last dose.

Total Symptom Score (TSS)

For each subject, the TSS will be computed as follows: The Baseline TSS is the average of the scores during the 28 to 35-day Screening period. Similarly, post randomization when there is at least 75% compliance during a 4-week period, the TSS is the average score for each 4-week period. The 4-week periods are Weeks 1-4 (Study Day 1-28), Weeks 5-8 (Study Day 29-56), and Weeks 9-12 (Study Day 57-84) and follows similarly for subjects whose involvement exceeds 12 weeks up to Week 24. If there is a delay in initiating study treatment, all TSS data prior to administering treatment will be included with the Screening period data. All TSS data post dose through Study Day 28 will constitute Weeks 1-4. If missing data in a 4-week period is due to lack of compliance or subject dropout, the TSS will be set to missing for the 4-week period. Missing data due to VOC, VOC hospitalization or RBC transfusion will be imputed as described

in Section 6.3.5. Compliance of at least 60% during each 4-week period will also be examined in a sensitivity analysis for TSS.

TSS₁₀₀ is TSS rescaled from a 27-point scale to 100-point scale. Algebraically, this is accomplished as follows:

$$TSS_{100} = TSS \times \frac{100}{27}.$$

Clinical Global Impression of Change

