6.3.4. Visit Windows

The blinded study period begins with the date of randomization, which is denoted in the protocol as Study Day 1. The conventions outlined below will be used to associate data measures, according to the study day corresponding to the date the data was collected, to an analysis visit window based on nominal (i.e., planned) visits, using the measure's study day relative to Day 1. Data collected before Study Day 1 will be considered screening information. Target study days, protocol acceptable ranges (per protocol) of study days for each scheduled assessment, and the analysis visit windows defined for each nominal visit day are shown in Tables 1 and 2.

If multiple assessments occur within a visit window, then the average of those assessments will be used for summarization and analysis.

Summarizations and analyses will utilize scheduled assessments and unscheduled assessments within a particular nominal window. Only central laboratory assessments will be included in summarizations and analyses of laboratory analytes.

Visit windows will be defined separately for non-PRO and PRO measures. PRO measures include ePRO Screening, ePRO SCD Severity Measure (SCDSM), eDiary data, EQ-5D-5L™, and CGI.

Table 1: Nominal Analysis Visit Windows for Non-PRO Measures

Nominal Visit Time	Target Study Day	Per Protocol Study Day Range	Study Day Range for Statistical Analysis*
Screening	-	[-35, -1]	[-35, -1]
Day 1	1	[-1, 1]	[-1, 1]
Week 2	14	[12, 16]	[2, 21]
Week 4	28	[26, 30]	[22, 35]
Week 6	42	[40, 44]	[36, 49]
Week 8	56	[54, 58]	[50, 70]
Week 12	84	[79, 89]	[71, 98]
Week 16	112	[107, 117]	[99, 126]
Week 20	140	[135, 145]	[127, 154]
Week 24	168	[163, 173]	[155, 210]
Week 36	252	[245, 259]	[211, 294]
Week 48	336	[329, 343]	[295, 378]
Week 60	420	[413, 427]	[379, 462]
Week 72	504	[497, 511]	[463, 545]

* Baseline is defined as the average of assessments on or prior the Study Day 1.

Table 2: Nominal Analysis Visit Windows for PRO Measures⁺

Nominal Visit Time	Study Day Range for Statistical Analysis[*]
Screening	[-35, -1]
Week 4	[1, 28]
Week 8	[29, 56]
Week 12	[57, 84]
Week 16	[85, 112]
Week 20	[113, 140]
Week 24	[141, 168]
Week 36	[169, 252]
Week 48	[253, 336]
Week 60	[337, 420]
Week 72	[421, 504]

* SCDSM scores on Study Days < -35 and Study Days > 168 will be excluded from SCDSM analyses

⁺ Notes:

(1) ePRO SCDSM is measured every day from the first day of Screening to Week 24 post randomization.

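### For the combined Group 1 and 2 analysis, the SAP summarizes the symptom score (SCDSM/TSS) descriptively only; an exploratory baseline-adjusted MMRM would add a voxelotor-placebo contrast with a CI at little cost

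*SAP*

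**What the plan says.** SAP 8.2.3.2 is a single sentence: "PRO measures, including Sick Cell Disease Severity Measure, EQ-5D-L health questionnaire, Clinical Global Impression (CGI), will be summarized descriptively". It names no model, treatment contrast, confidence interval or covariate. The symptom score does not appear in the fixed sequence of SAP 6.3.3.

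Elsewhere the SAP treats the score in detail. Section 4: "The Baseline TSS is the average of the scores during the 28 to 35-day Screening period". The notes to Table 2 in 6.3.4: "ePRO SCDSM is measured every day from the first day of Screening to Week 24 post randomization". Section 6.3.5.3 gives rules for missed diary days, VOC, VOC hospitalization and transfusion, with an order in which to apply them. Sections 4 and 6.3.5.3 add sensitivity analyses with a 60% compliance threshold and a 12-week transfusion window.

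The protocol says more about the model:

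- Protocol 8.4.2.3, on missing TSS data and not limited to any group: "For the primary method of analysis of this endpoint (MMRM), missing at random (MAR) is assumed and no imputation will be done".
- Protocol 8.4.1.2.2, last paragraph, which opens "For Group 1 analysis, the proportion of days with SCD exacerbation will be analyzed by a fixed effects linear model" and continues "Change from Baseline in the TSS will be analyzed with an MMRM".
- Protocol 8.4.1.3 lists EQ-5D and CGI as descriptive by treatment group. The SCDSM is not in that list.

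On purpose, SAP section 3 says "The exploratory objectives are to evaluate the effects of voxelotor compared to placebo on the following", and the SCDSM heads the list. Protocol 2.2 justifies the placebo arm in particular by the SCDSM, "which requires a placebo group for interpretation for the meaningfulness of changes in symptoms". SAP section 2 gives SAP version 5.0 precedence over the analysis text of Protocol Amendment 4.

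**The concern.** The exploratory objective is comparative, and a daily baseline of at least four weeks is collected for the score. A descriptive summary leaves the reader to form the between-arm comparison. The sensitivity rules for compliance and transfusion then have no specified contrast to test.

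Two things are at stake, both secondary to the primary inference. One is precision: a well-measured baseline is available and is not specified for adjustment. The other is pre-specification. Treatment codes for 156 subjects had already been opened to sponsor biostatistics (SAP sections 2 and 6.2), and SAP section 10 asks only that analyses outside the SAP be identified as such. A TSS contrast requested later would be post hoc. One written in before the 118 subjects of Group 2b are unblinded would not carry that label to the same degree.

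**Working it through.** **The plan's own figures.** The documents give no sample size, effect, SD or power for TSS. The number per arm comes from the power statement for the primary endpoint (SAP 6.1): about 90 per arm, 40% against 10%, Fisher's exact test, two-sided alpha 0.0481, power above 95%. Exact enumeration gives 0.997, so that statement reproduces. The worked TSS example in SAP 6.3.5.3 also reproduces: (6×20 + 22×21)/28 = 20.79 and (7×21 + 21×12)/28 = 14.25.

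**The passages side by side.**

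| Endpoint | Status in SAP | Specified analysis |
|---|---|---|
| Hb change (8.2.1.2) | secondary | MMRM, baseline Hb as covariate, stratification factors |
| Hemolysis measures (8.2.2.1) | secondary | similar MMRM |
| School/work attendance (8.2.3.3) | exploratory | ANOVA with stratification factors |
| SCDSM/TSS (8.2.3.2) | exploratory | descriptive |

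An exploratory diary endpoint is modelled, so exploratory status alone does not explain why TSS is not.

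**What adjustment would gain.** The comparator is an unadjusted difference in mean change from baseline, which a reader could derive from descriptive tables of change by arm. Work in units of the TSS standard deviation, for one 4-week period with complete data. Let r be the correlation between baseline and follow-up. It is not in the documents; 0.5 to 0.8 is an assumption.

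- SE of a raw follow-up difference: √(2/n). With n = 90, √(2/90) = 0.149, and 1.96 × 0.149 = 0.292.
- Change-score contrast: multiply by √(2(1−r)).
- Baseline-adjusted contrast: multiply by √(1−r²).
- Ratio of adjusted to change-score width: √((1−r²)/(2(1−r))) = √((1+r)/2).

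| r | Half-width, change score (SD) | Half-width, adjusted (SD) | Ratio | CI narrower by |
|---|---|---|---|---|
| 0.5 | 0.292 | 0.253 | 0.866 | 13% |
| 0.6 | 0.261 | 0.234 | 0.894 | 11% |
| 0.7 | 0.226 | 0.209 | 0.922 | 8% |
| 0.8 | 0.185 | 0.175 | 0.949 | 5% |

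Protocol 8.4.2 anticipates dropout below 10%. At 81 per arm (90 × 0.9) the adjusted half-width runs from 0.267 (r = 0.5) to 0.185 SD (r = 0.8). The percentage gains do not change, because n cancels in the ratio.

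A mixed model also uses the other periods of a subject who has one period set to missing. That effect depends on the missingness pattern and is not quantified here.

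**The case against.** The strongest case on the other side is that the SAP does what it is entitled to do. It supersedes the protocol, the SCDSM is exploratory in the endpoint lists of both documents, and SAP section 8 makes descriptive methods the default and confines hypothesis testing to 6.3.3. The key-secondary label in Protocol 2.2 conflicts with those lists and carries little weight. All of this stands, and it is why the point is an improvement only.

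A reader might also infer several stronger things that the documents do not support:

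- *That the trial plans no modelled TSS comparison at all.* Protocol 8.4.1.2.2 plans an MMRM for Group 1, and SAP section 2 says the Group 1 Analysis (62 subjects) included PRO endpoints. The gap concerns the combined analysis.
- *That the SAP withdraws a baseline-adjusted model the protocol had promised.* Protocol 8.4.2.3 is a missing-data rule that mentions the MMRM in parentheses. No protocol text sets out its terms for Groups 1 and 2 combined, and none names baseline TSS as a covariate.
- *That the descriptive summary ignores baseline.* SAP section 4 defines baseline TSS and change from baseline generally, and 8.1 tabulates baseline TSS. The tables may well show change.
- *That missing periods are disregarded.* SAP 6.3.5.3 imputes gaps due to VOC and periods after transfusion, and adds sensitivity rules.
- *That adjustment gains 13% to 40% in interval width.* That range is against raw follow-up means, which the SAP does not specify as its contrast.
- *That an MMRM would cure selective diary completion.* It would not if completion depends on unobserved symptoms.

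Finally, the end of the SAP, where its contents place the output lists, is blacked out, so a modelled TSS output there cannot be excluded. The point rests on the methods text.

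**Conclusion.** The point holds as a low-cost improvement. For the 274-subject analysis, the SAP's methods text specifies no baseline-adjusted dose-placebo contrast with a CI for TSS, although Protocol 8.4.2.3 calls an MMRM the primary method and the SAP retains the rules that such a model would use. It is not an error: the primary analysis, type I error control and the fixed sequence are untouched.

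The gain in CI width is about 13% to 5% against an unadjusted change-score contrast. This rests on an assumed correlation of 0.5 to 0.8, equal variances at baseline and follow-up, and about 90 subjects per arm for the absolute widths. The larger practical benefit is a contrast that is defined in advance. No effect on any trial conclusion is shown.

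**What to change.** In SAP 8.2.3.2, add an MMRM of change from baseline in TSS over the six 4-week periods to Week 24. Use fixed terms for treatment, period, treatment-by-period, baseline TSS, HU use, age group and region, with an unstructured within-subject covariance (6×7/2 = 21 parameters). This mirrors the Hb model in 8.2.1.2. Report each dose-placebo difference with a 95% CI, label it exploratory and outside the fixed sequence of 6.3.3, and apply the existing 60% compliance and 12-week transfusion sensitivity rules to it. Keep the descriptive tables and say that they are by treatment group.

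The cost is one model and one table, with no new data and no alpha. The remaining weakness is the missing-at-random assumption, which should be stated beside the result: it does not remove bias if diary completion depends on unobserved symptoms.
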